### 5.1.6 Labeling, Packaging, Storage, and Handling

[figure not shown]
The study drug will be shipped to a designee at the study site and must be stored in a pharmacy or locked and secured in a storage facility with temperature control, accessible only to those individuals authorized by the investigator or designee.

The Sponsor will supply sufficient quantities of IV GMI-1070 and placebo to allow completion of this study. Study drug will be supplied to the pharmacy in vials containing 8.3 mL of sterile solution for IV administration. Active vials will contain GMI-1070 at 30 mg per mL.

All labeling will meet applicable regulatory requirements. Sample labels are below:

Placebo will be provided as vials containing 8.3 mL of sterile vehicle (phosphate-buffered saline [PBS], with a pH of 6.5).

Study drug must be refrigerated at a controlled temperature between 2° and 8° C. The investigator or designee is responsible for ensuring that the temperature is monitored throughout the total duration of the trial and that records are maintained; the temperature should be monitored continuously. Excursion from the established range will require site investigation as to cause and remediation. GMI will determine the ultimate impact of any excursions and will provide supportive documentation.

### **5.1.7 Compliance and Drug Accountability**

Study drug must be used only as directed in the protocol. Study drug inventory and accountability forms will be maintained by the pharmacist or designee, and examined and reconciled by the unblinded monitor.

Study drug may not be relabeled. Study drug will not be destroyed or returned without explicit written instructions from the Sponsor. The Investigator must not dispense the study drug from, nor store it at, any site other than the study sites agreed upon with the Sponsor and approved by the IRB/IEC. Based on entries in the site drug accountability forms, it must be possible to reconcile drug delivered with that used and returned. All study drug must be accounted for and all discrepancies investigated and documented appropriately.

### **5.2 Concomitant Treatments**

Treatments intended for other indications should be administered as usual. All concomitant treatments taken during the study (within 48 hours of randomization to the last post-dose follow-up assessment) should be recorded in the source document and CRF. All concomitant treatments should be confirmed and reviewed by the investigator or his/her designee prior to each dose for the duration of the study. Subjects taking systemic steroid therapy within 48 hours prior to enrollment, or those at baseline who have an expectation that therapy may be used during the study, will be excluded from enrollment. The use of inhaled or topical steroids, hydroxyurea, and NSAIDs will be allowed.

For the purposes of inclusion/exclusion, the term “illicit drugs” includes, but is not limited to, cocaine, heroin, ecstasy, and phencyclidine (commonly known as ‘PCP’). The use of marijuana is not excluded for the purposes of this study. Investigators are encouraged not to enroll subjects for whom addiction to prescribed opioids may interfere with interpretation of study endpoints.

Females of childbearing potential must be abstinent or agree to use one medically reliable method of contraception throughout the study period and for 30 days after the last dose of study drug. Acceptable methods include intrauterine devices, hormonal contraceptives (oral, depot, patch, or injectable), double barrier methods such as condoms or diaphragms with spermicidal gel or foam, or a surgically sterilized partner (vasectomy for 6 months minimum). If hormonal contraceptives are used, they should be taken according to the package insert. Women of child-bearing potential who are not currently sexually active must agree to use an acceptable method of contraception, as defined above, if they decide to become sexually active within 30 days after the last dose of study drug.

Sexually active male subjects should ensure that an acceptable method of contraception is used throughout the study period and for 30 days after the last dose of investigational product. Acceptable contraceptives include double barrier methods

such as condoms with spermicidal gel or surgical sterilization (eg, vasectomy for 6 month minimum).

### **5.2.1 Pain Management**

Pain management should be approached according to the institution's usual procedures, with the following suggestions for standardized management:

- Recommended IV pain medications include morphine (preferred), hydromorphone, ketorolac, or fentanyl, used in accordance with standard clinical practice
- Initial treatment should aim to achieve pain control; pain control is defined as pain that does not require further escalation of pain medication OR subject reports pain is controlled
- Ongoing treatment should aim to maintain pain control; consider weaning IV opioids once pain is controlled ( $\leq 7/10$ )
- Discharge criteria related to pain may include improved pain score; on oral hydration; and on oral pain medications for at least 6 hours
- Patient-controlled analgesia (PCA) use (basal and bolus dosing) is encouraged for all subjects, per hospital procedure
- Subjects will be adequately hydrated per routine procedure and as medically indicated

Discharge instructions for pain management should include a minimum of 48 hours continuous treatment with oral opioid or similar pain medications. Subjects on chronic opioids may require different instructions, such as an opioid weaning regimen.

### **5.2.2 Transfusion**

In all cases, the medical judgment of the responsible physician will determine the course of treatment.

The following suggestions are made for standardized management of transfusions in study subjects:

- Uncomplicated pain episodes generally do not require transfusion for treatment
- Conditions which may require transfusion as determined by the physician include: acute neurologic event, severe pneumonia or severe acute chest syndrome, acute arterial hypoxia ( $\text{PaO}_2 < 70$  mmHg), severe anemia with cardiac decompensation, and/or symptomatic anemia (such as subjective shortness of breath or postural dizziness), worsening of anemia with an inadequate reticulocyte response, splenic or hepatic sequestration

## **6 STUDY PROCEDURES AND EVALUATIONS**

## **6.1 Study Procedures**

Refer to Table 1, for a list of procedures and times for assessments, and to Table 8 and Table 9 for a list of PK and biomarker assessments.

### **6.1.1 Pre-study Identification of Potential Study Subjects**

Investigators are encouraged to identify subjects with VOC who are likely to be admitted, and approach them for consent and eligibility criteria early in the process of VOC care. Subjects with a history of frequent admissions for painful VOC in the past 12 months, and identified during routine clinical care as potentially eligible for study participation, may be approached with educational information about the study. Such education will not replace the need to obtain informed consent (and assent, where applicable) in accordance with applicable regulations and ICH E6 prior to administration of any study related procedures.

Where possible and as appropriate, subjects who are eligible for study participation should have admission procedures expedited to allow for early study enrollment and prompt management of VOC per study procedures.

All subjects should be dosed with the first dose of study drug within 24 hours of initial medical evaluation in the Emergency Department/clinic. Any initial dose of study drug administered more than 24 hours after initial medical evaluation will be considered a protocol deviation.

### **6.1.2 Pre-dose Baseline**

Subjects will sign the informed consent form (and assent, where applicable), and eligibility will be determined. Eligible subjects will be randomized to a treatment group.

Sampling for biomarkers and IVM will be initiated at selected investigational sites.

Results of all eligibility assessments, particularly clinical laboratories and pregnancy tests, and radiographs where applicable, should be reviewed by the investigator or qualified designee before randomization and dosing with study drug is initiated. Eligible subjects will be randomized in a 1:1 ratio to treatment (either GMI-1070 or placebo) using an IVRS.

Note – A sample will be drawn for hemoglobin electrophoresis at baseline, but the result is not required prior to randomization or first dose.

### **6.1.3 Visit 1**

Visit 1 is considered to be the period of hospitalization, during which subjects will be dosed and samples will be obtained for PK assessments and, where applicable, biomarkers and IVM.

All subjects should be dosed with study drug within 24 hours of initial medical evaluation in the Emergency Department/clinic at the latest. Dosing will continue q12 hours until study drug is discontinued. The weight measured at Baseline will be used to determine the appropriate dose administered throughout the study. Study drug will be administered as described in Section 5.1.2.

Results of all assessments, particularly AEs and VAS scores, should be reviewed by the investigator or qualified designee on a daily basis after dosing with study drug is initiated. At a minimum, this review will be documented by the reviewers dated initials.

The calendar date and 24-hour clock time of the beginning and end of each infusion will be recorded in the medical record and on the CRF.

PK sampling will commence as described in Section 6.4. Biomarker and IVM sampling will commence at selected sites. AE and concomitant medication information will be collected during this period.

Subjects who remain hospitalized after Day 7 will undergo the following assessments for each additional day of hospitalization up to Day 28:

- Days 8 to 12: Same assessments expected for Days 1 to 7 (Visit 1).
- Days 13 to 28: Same assessments expected for Days 1 to 7 (Visit 1) with VAS scores collected daily instead of q4 hours.
- Visits 2, 3, 4 should be completed at the assigned times whether the subject is discharged from the hospital or remains hospitalized.

#### **6.1.4 Visit 2**

Visit 2 will occur  $36 \pm 12$  hours after the last dose of study medication, during which time the subject may or may not still be hospitalized.

#### **6.1.5 Visit 3**

Visit 3 will occur  $7 \pm 3$  days after the last dose of study medication.

**6.1.6 Visit 4**

Visit 4 will occur  $28 \pm 5$  days post last dose and is the last follow-up for the study.

**6.2 Efficacy Evaluation**

Resolution of VOC will be assessed via a 10 cm VAS scale (to be provided with the CRF), IV opioid and IV NSAID use, readiness for hospital discharge, and time of actual hospital discharge.

VAS data will be recorded a minimum of every 4 hours (while awake) throughout the inpatient study period. Subject pain cards will be provided for use at each pain assessment. The subject will be asked a general question, such as, "how is your pain now?" and the subject will record the answer on a continuous pain scale. The card will be placed in the source record.

**6.3 Safety Evaluations****6.3.1 Physical Examination**

A full physical examination includes a review of the following body systems:

- general appearance
- skin
- head, ears, eyes, nose, throat
- spine/neck/thyroid
- respiratory
- cardiovascular
- abdomen (including liver and kidneys)
- nervous system
- musculoskeletal

A targeted physical examination includes body systems selected at the discretion of the investigator. At a minimum, this will include respiratory, cardiovascular, and abdominal examinations. Additional examination components may be added at the discretion of the investigator.

Any abnormalities or changes in intensity noted during the review of body systems should be documented and reported in the medical record and on the appropriate CRF page. If a new clinically significant finding occurs at the time of or subsequent to dosing, an AE form must be completed. In addition, resolution of any abnormal, clinically significant findings during the study will be noted in the medical record and the CRF.

### **6.3.2 Vital Signs**

Complete vital signs are considered to be body temperature, respirations, blood pressure, and pulse (taken after 5 minutes seated or supine). Oxygen levels may be included as appropriate.

During Visit 1 vital signs should be recorded pre- and post-dose. Otherwise, when the time of vital signs measurement coincides with a blood draw, the vital signs will be taken before the scheduled blood draw.

Abnormal vital signs are not to be considered AEs unless thought to be clinically significant by the investigator or treating physician. The sponsor will routinely evaluate vital signs to investigate possible emerging trends.

### **6.3.3 Clinical Laboratory Evaluations**

All laboratory assays will be performed locally according to the laboratory's normal procedures. Reference ranges will be supplied by the local laboratory. Laboratory assays may be repeated once to rule out laboratory error, before determining if results are normal or abnormal. It is recognized that in SCD, laboratory values that are out of the reference range may in fact be baseline for that individual. When test results are outside the reference range, the investigator (or his/her sub-investigator) will indicate on the medical record/laboratory report and on the CRF whether the result is considered to be clinically significant or not. Out of range results not considered to be clinically significant by the investigator (or his/her qualified sub-investigator) will not be considered abnormal for the purposes of this study. Abnormal laboratory values (out of range and clinically significant) which are unexpected or not explained by the subject's clinical condition and which are a worsening from the subject's baseline should be repeated until confirmed, explained, or resolved, and should be reported as AEs. The sponsor will routinely evaluate clinical laboratory findings to investigate possible emerging trends. If urinalysis is positive for blood, protein, or leukocyte esterase, a microscopic examination for RBC, WBC, bacteria, and casts will be performed.

Data to be collected are noted below. Collection for clinical laboratory evaluations will occur once daily and time of collection must be recorded in the CRF.

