##### **6.3.5.1 Definition of Adverse Events**

An AE is any untoward medical occurrence in a subject administered a pharmaceutical product that does not necessarily have a causal relationship with this treatment. Adverse events may be reported by the subject, discovered by investigator questioning, or detected through physical examination, laboratory test, or other means.

AEs include (International Conference on Harmonization E2A):

- Any new undesirable medical experience or an unfavorable and unintended change of an existing condition that occurs during or after treatment, whether or not considered related to study drug
- Abnormal laboratory findings considered by the investigator to be clinically significant, ie, those that are unusual for the populations being studied or individual subject

The subjects will be instructed to inform the investigator or clinical staff of any AEs and intercurrent illnesses experienced during the trial. The inquiry will be posed in a non-specific manner using open-ended questions so as not to bias the response (eg, “How are you today?” or “How have you been since your last visit?”). Any subject who has an AE will be evaluated by the investigator and will be treated.

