#### **6.3.6.1 Disease Related Adverse Events (DRAEs)**

It is recognized that VOC and pain are frequent and expected events in SCD, and will be present at baseline in all subjects enrolled in this study. Fluctuations in pain are the expected and usual course of VOC and will not be reported as AEs. Pain and fluctuations in pain will be collected as part of the primary study objective, and evaluated extensively in the efficacy analysis. Changes in pain resulting from causes other than VOC should be reported as AEs. The use of opioids for VOC episodes is usually required and considered routine. Subjects being admitted to the hospital for VOC will be expected to receive IV opioid or IV pain medications for treatment of the VOC. It is also recognized that subjects being discharged from the hospital for VOC will go home with prescribed opioid and other pain medications.

After discharge from the hospital following a VOC episode, subjects often have recurrent or repeat episodes of VOC. For the purposes of this study, after discharge from the hospital for the original event, VOC (new or recurring) shall be defined as an episode requiring a visit to a medical facility resulting in medical treatment for pain. When determining grade of an AE for new or recurring VOC, the investigator shall use the classification noted below.

- Mild: the pain can be managed at home (includes home oral opioid pain medication)
- Moderate: the pain requires medical intervention (includes clinic, day hospital, or emergency department care)
- Severe: the pain requires inpatient treatment

Patients with SCD, as a result of this condition, commonly have abnormal laboratory values and clinical findings. It is assumed that abnormalities in physical exam or laboratory findings consistent with the subject's underlying diagnosis of SCD or VOC will be present prior to dosing and therefore will not be treatment-emergent AEs (TEAEs).

In general, symptoms of SCD should not be classed as AEs if they are within the normal day-to-day fluctuation expected for the disease. However, significant

worsening of the symptoms should be recorded as an AE. Therefore, DRAEs that are also TEAEs will be reported as AEs per study procedures.

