### **6.3.6.2 Vital Signs and Clinical Laboratory Evaluations**

Abnormal vital signs are not to be considered AEs unless thought to be clinically significant by the investigator or treating physician.

Abnormal laboratory values which are out of range and clinically significant and which are a worsening from the subject's baseline should be reported as AEs. When evaluating such changes, the extent of deviation from the reference range or a subject's baseline value, the duration until return to the reference range/baseline, either while continuing treatment or after the end of treatment with the investigational product, and the range of variation of the respective parameter within its reference range, must be taken into consideration.

The investigator should decide, based on the above criteria and the clinical condition of a subject, whether a change in a vital sign or laboratory parameter is clinically significant and therefore represents an AE.

The Sponsor Medical Monitor will routinely evaluate clinical laboratory findings and vital signs to investigate possible emerging trends.

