### 8.2.4.2 Disease Related Adverse Events (DRAEs)

Disease related adverse events (DRAEs) are defined as AEs that occur during a subject's participation in the study, but which are expected for the condition (SCD, VOC), and may include:

- anemia (down to Hb  $\geq 5$ )
- elevated WBC count (up to WBC  $\leq 20,000/\text{mm}^3$ )
- unconjugated hyperbilirubinemia
- elevated markers of hemolysis (AST and LDH)

- proteinuria
- hematuria
- hypertension
- VOC-related swelling/erythema/warmth of an extremity
- nausea/vomiting/constipation
- low fever under 101.5° F
- dehydration
- pruritus
- increased somnolence
- fall in reticulocyte count

DRAEs will be reported and analyzed as AEs per study procedures. In addition to the analysis of all AEs per the section above, DRAEs will be analyzed by treatment group.

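### Sections 6.3.3 and 6.3.6.2 set different tests for reporting a laboratory change as an AE, and the stricter test does not fit the planned count of expected disease-related events

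*Protocol*

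**What the plan says.** Several parts of the protocol decide whether a post-dose laboratory change becomes an AE.

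- **6.3.3** calls for repeat testing and AE reporting of worsened values that are "out of range and clinically significant) which are unexpected or not explained by" the subject's clinical condition.
- **6.3.5.1** includes among AEs laboratory findings judged clinically significant, and explains this as "those that are unusual for the populations being studied or individual subject".
- **6.3.6** requires a new AE report when an untoward event that was present before treatment worsens to a clinically significant degree after study drug starts.
- **6.3.6.1** assumes that examination or laboratory abnormalities consistent with SCD or VOC "will be present prior to dosing and therefore will not be treatment-emergent AEs". The same section ends by saying that "DRAEs that are also TEAEs will be reported as AEs per study procedures".
- **6.3.6.2** calls for AE reporting of laboratory values "which are out of range and clinically significant and which are a worsening from" the subject's baseline. It sets no condition about expectedness or explanation.
- **8.2.4.2** defines DRAEs as AEs that arise during participation "but which are expected for the condition (SCD, VOC), and may include" 14 bulleted items. It then states that "DRAEs will be reported and analyzed as AEs per study procedures", with a further analysis by treatment group.

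**The concern.** Sections 6.3.3 and 6.3.6.2 speak to the same investigators about the same daily samples. One makes reporting turn on whether the change is unexpected or unexplained; the other does not. A laboratory DRAE is expected by definition and will often be explained by the crisis, so it is the kind of event on which the two sections part.

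What is at stake is the comparability of safety counts. The TEAE tables and between-group tests in 8.2.4.1, the DRAE analysis in 8.2.4.2 and the AE part of the DSMB reviews (6.3.6.4, 8.2.7) all start from what sites enter as AEs. With approximately 20 sites, those counts would partly reflect which section each site applied.

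Raised WBC shows why this matters. Section 1.7.1 reports small mean rises in WBC and neutrophils 24 hours after dosing in study GMI-1070-103, with one moderate leukocytosis AE judged probably related. It adds that such a rise would be predicted from the drug's selectin-inhibiting mechanism. Raised WBC up to 20,000/mm³ is also a listed DRAE. A plausible drug effect therefore sits in the category that 6.3.3 lets a site attribute to the disease.

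**Working it through.** No sample size, power or alpha figure bears on this point. The check is a count of the DRAE list and a side-by-side reading of the rules.

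**Count of the list in 8.2.4.2.**
- Laboratory findings (7): anemia; elevated WBC; unconjugated hyperbilirubinemia; elevated AST and LDH; proteinuria; hematuria; fall in reticulocyte count.
- Clinical or vital-sign findings (7): hypertension; swelling, erythema or warmth of an extremity; nausea, vomiting or constipation; low fever; dehydration; pruritus; increased somnolence.
- Laboratory share: 7/14 = 50%. Counting AST and LDH separately gives 8/15 = 53%. Also splitting the nausea, vomiting and constipation bullet gives 8/17 = 47%.

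**One illustrative event taken through the rules.** Suppose a subject's WBC rises after dosing to a value out of range and above that subject's baseline, but below 20,000/mm³. The investigator judges it clinically significant and attributes it to the crisis.

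| Section | Result |
|---|---|
| 6.3.3 | Expected and explained by the condition, so outside the stated reporting criterion |
| 6.3.5.1 | Not unusual for the population; may be unusual for this subject, or an unfavourable change in an existing condition; arguable |
| 6.3.6 | AE, if the baseline elevation counts as a pre-treatment untoward event that worsened |
| 6.3.6.1, laboratory assumption | Presumed to pre-date dosing, so not a TEAE |
| 6.3.6.1, last sentence | Reported if it is a TEAE, which the assumption above has just denied |
| 6.3.6.2 | AE |
| 8.2.4.2 | DRAE, counted and compared by group |

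The same event is therefore reportable under 6.3.6.2, outside the reporting criterion in 6.3.3, and presumed not treatment-emergent in 6.3.6.1.

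**Whether 6.3.6.1 settles it.** Its closing sentence reaches only DRAEs that are TEAEs, and its assumption about laboratory findings narrows that group first. Its instruction to record significant worsening refers to symptoms, not laboratory values. Section 8.2.4.1 defines a TEAE by onset on or after dosing, which is a matter of fact. Table 1 already schedules clinical laboratories and urinalysis before the first dose, so pre-existence can be checked for each subject and need not be assumed.

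**The case against.** The best defence is that the protocol, read as a whole, already requires these events to be reported. Section 6.3.6.2 has no expectedness condition. Section 6.3.6 makes reporting of clinically significant worsening mandatory. Section 6.3.5.1 also admits values unusual for the individual subject and any unfavourable change in an existing condition. Section 6.3.6.1 ends by sending treatment-emergent DRAEs to AE reporting. Section 6.3.3 says which values to report and does not expressly forbid reporting others. A DRAE is, on the wording of 8.2.4.2, a label on something that is already an AE.

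Much of this stands, and it rules out stronger readings that a reader might infer:

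- *The protocol admits only unexpected laboratory values as AEs.* It does not; 6.3.6.2 and 6.3.6 plainly admit expected ones.
- *Half of the DRAE list will go uncounted.* Seven of 14 is a count of item types, not of lost events. It is an upper bound, reached only where a site treats 6.3.3 and the 6.3.6.1 assumption as decisive and sets the other sections aside.
- *The Grade 4 anemia in study 103 shows what would be missed.* Section 1.7.1 describes it as only remotely related to study drug. It was severe, symptomatic and needed transfusion, so it is an unlikely event to pass as routine.
- *The safety data are lost.* Section 8.2.4.3 still summarises laboratory values and lists clinically significant results, and the Medical Monitor reviews laboratory data under 6.3.6.2 and 6.3.6.4.

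What the defence does not remove is the disagreement itself. No text ranks 6.3.3 against 6.3.6.2, so a site following 6.3.3 has followed the protocol. The summaries in 8.2.4.3 describe values; they do not supply the severity grade and relationship assessment that accompany an AE.

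**Conclusion.** The laboratory AE criteria in 6.3.3 and 6.3.6.2 differ. The 6.3.3 condition, together with the assumption in 6.3.6.1, cannot be squared with 8.2.4.2, with the worsening rule in 6.3.6 or with the last sentence of 6.3.6.1. AE and DRAE counts for seven of the 14 listed items could depend on the section a site follows, with under-reporting of up to all seven where 6.3.3 and 6.3.6.1 are applied literally.

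This rests on two assumptions: that sites differ in which section they apply, and that investigators attribute at least some clinically significant changes to the disease. The protocol gives no expected DRAE incidence, so the number of events affected cannot be computed. Under the blind there is no evident reason for under-reporting to favour one arm; the likelier effect is to obscure a real difference. The point concerns the AE and DRAE tables, not the efficacy analysis. It should be corrected in the protocol: an SAP can re-tabulate laboratory values, but it cannot restore AE reports that sites never made.

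**What to change.** Bring 6.3.3, 6.3.5.1, 6.3.6.1, 6.3.6.2 and 8.2.4.2 to one criterion. The protocol's own 6.3.6.2 rule serves: an out-of-range, clinically significant worsening from the subject's own baseline is an AE, whether or not it was expected.

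- **6.3.3:** keep the unexpected-or-unexplained condition only as the trigger for repeat testing, and refer to 6.3.6.2 for AE reporting.
- **6.3.5.1:** align the explanation of clinical significance with that rule, so that being usual for the population does not by itself exclude a worsening.
- **6.3.6.1:** replace the assumption of pre-existence with a comparison against the pre-dose sample that Table 1 already collects.
- **8.2.4.2:** state that events meeting the rule and expected for SCD or VOC carry the DRAE flag within the AE data.

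The cost is wording and some additional AE entries at sites. No new assessment or sample is needed.
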